We still do not know enough about how a focal lesion impacts the dynamics within brain circuits that govern motor learning and how this relates to maladaptive plastic changes. Filling this knowledge gap builds the basis for designing interventions that causally target experience-dependent maladaptive changes which negatively impact the patient's recovery (e.g., leading to disuse of the paretic hand). With this JI project, we will generate pilot data serving as the first evidence for motor learning-related network dynamics in the chronic phase after stroke (aim 1) and their link with biomarkers of recovery of upper-extremity sensorimotor function (aim 2).

AIM 1 To characterize motor learning (ML)-related neural network dynamics in the presence of a focal lesion, we will use a representational statistical modeling approach¹⁸ to describe learning-related connectivity changes based on task-based functional magnetic resonance imaging (fMRI) in stroke survivors (≥ 6 months post-lesion, stroke group SG) and healthy volunteers of comparable age and gender (control group, CG). Functional connectivity patterns will be modeled throughout the acquisition phase to capture the temporal trajectory of encoding-related network changes.

AIM 2 To understand the association between ML-related network dynamics and biomarkers of recovery, we will comprehensively describe upper-extremity sensorimotor functioning and impairment for the individuals in the SG and statistically integrate these biomarkers of recovery with the ML-related network dynamics within a separate representational model.

B. BACKGROUND AND SIGNIFICANCE

Recovery of upper extremity function remains dissatisfying for the majority of stroke survivors with sensorimotor impairment¹⁹, which represents a major hindrance to independence in daily life²⁰. Within the field of rehabilitation research, learning mechanisms have long been a major area of interest because they are considered one key player in functional recovery. This basic premise goes back to seminal work that established the brain's capacity to change in response to environmental stimuli and learning, i.e., experience-dependent plasticity^{21,22}.

However, it is evident that plasticity does not have purely beneficial effects on recovery³ but that also negative consequences such as learned disuse of the paretic hand can be observed¹.

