The proposed JI project implements a conceptually and methodologically innovative approach to characterize stroke-related alterations within functional circuits that govern sensorimotor learning and their link to recovery. The completion of this project will set the stage for the PI's planned next steps. Altered network dynamics during learning in the SG will provide network-informed targets for non-invasive brain stimulation to further investigate their modifiability and behavioral relevance. Additionally, they justify the longitudinal investigation of network dynamics within learning circuits during the development of maladaptive plastic changes longitudinally in the early phase after stroke.

C. PRELIMINARY STUDIES

The project describes a pilot study and serves as a proof-of-concept to generate preliminary data to support the planned follow-up R01 proposal.

D. RESEARCH DESIGN AND METHODS (including data analysis)

D1. OVERVIEW OF STUDY STRUCTURE AND PROCEDURES

D1.1 Sample Size Rationale & Recruitment Feasibility.

Before the main study described below, a short series of pilot experiments is planned to iteratively test the experimental paradigm with the goal to assure feasibility of all experimental procedures for varying levels of motor-functional capacity in the stroke group.

Initial pilot phase. For this initial phase, which precedes the main study, we anticipate recruiting a maximum of N=40 volunteers (patients and controls) to iteratively test and optimize the paradigm (the learning task) for use in the MRI environment.

Main study. Target recruitment will include N=25 stroke survivors in the chronic phase (≥ 6 months after index lesion, stroke group) and N=15 healthy volunteers of comparable gender, age range and education level (control group). There will be no overlap with individuals of the initial pilot phase. Based on previous work, we anticipate that with these sample sizes it will be sufficient to determine the feasibility and effect sizes for the planned follow-up R01 application (also see Sample Size Justification below).

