For the learning task-based data, a general linear model (GLM) will be fitted to each individual's data serving as the basis for the representational similarity analysis (RSA). In addition to the regressors of interest (matched to the onset time of each regressor of the event-related design of the learning-paradigm: 1st and 2nd order sequence force cues, random force cues) six motion parameters will be included as nuisance covariates. Estimated beta-values will be extracted from the GLM for each stimulus and run for each region of interest (ROI) within subject. For each ROI, a neural matrix will be created by correlating (Pearson) the multi-voxel patterns between all possible combinations of pairs of stimuli of the learning task condition and then averaged across subjects within group (first-order RSA⁵¹). In the second step, group-averaged matrices (only the upper diagonal elements) will be vectorized and correlated (Pearson) for all possible combinations of ROI pairs (second-order RSA⁵¹), which will allow to investigate the representational similarity between ROIs i.e., the clustering/networks of ROIs, with regard to the between-condition similarity in multi-voxel activation patterns.

For the resting-state data, the connectivity analysis will be used to identify physiological biomarkers for recovery and potential predictors for learning efficiency. For this purpose whole-brain resting-state network fluctuations, based on BOLD signal time courses, will be extracted for cortical and subcortical ROIs. Nuisance regression will be performed to account for the effects of motion on functional connectivity (including six translation and rotation parameters from the motion correction transformation, average CSF, white matter, and whole-brain time courses, as well as the first derivatives, squares, and squared derivatives of each of these confound predictors⁵². To extract the dynamic modulation of connectivity over time, time courses will be divided into sub-blocks of multiples of the TR to allow capturing slow-frequency fluctuations by approximating the frequency envelope of the hemodynamic response at the given TR with the highest possible temporal precision. Connectivity will be quantified as the magnitude-squared coherence^{53,54} between each pair of ROI for each sub-block of time⁵⁵. Network characteristics and their temporal dynamics will then be analyzed with dynamic network statistics following the approach given in reference⁵⁵.

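### D3.2 computes second-order r from averages of 25 stroke and 15 control matrices, so the two groups' values are not directly comparable, and the direction of the distortion is unknown

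*Combined protocol and SAP*

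**What the plan says.** D3.2 (Analysis Plan, task-based data) builds one stimulus-by-stimulus correlation matrix per ROI and participant. These matrices are computed "and then averaged across subjects within group". In the second step, "group-averaged matrices (only the upper diagonal elements) will be vectorized and correlated (Pearson) for all possible combinations of ROI pairs". The stated purpose is within-group: "which will allow to investigate the representational similarity between ROIs", that is, how ROIs cluster into networks.

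The group sizes are in D1.1. "Target recruitment will include N=25 stroke survivors in the chronic phase", together with "N=15 healthy volunteers of comparable gender, age range and education level".

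D3.2 gives no equal-n step, reliability correction, noise ceiling, permutation scheme or participant-level second-order r. It also names no stroke-control test of these values. The comparison is implied elsewhere. Aim 1 studies learning-related connectivity in stroke survivors and in "healthy volunteers of comparable age and gender (control group, CG"). Section B says that altered dynamics in the stroke group will supply targets for brain stimulation, and the controls are the only reference against which they could be called altered. D3.1 adds that a main goal is to obtain effect sizes for the next grant proposal.

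**The concern.** An average of 25 noisy matrices is more reliable than an average of 15. A correlation between two such averages therefore has an expected value that depends on the group size as well as on the true similarity between the ROIs. With 25 and 15 averaged, the two groups can show different second-order r when the true structure is the same in both.

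This is a property of the point estimate. It is present even if the group values are only described, so it is separate from the question of how to test them. At stake are the reading of the stroke network as altered or not, the stimulation targets drawn from that reading, and the effect sizes carried into the follow-up proposal.

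**Working it through.** **Inputs from the protocol.** n = 25 and n = 15 (D1.1); averaging within group before the second-order step, and Pearson r between ROIs (D3.2). The plan states no value for second-order r, so there is no figure to reproduce. The range 0.33 to 0.52 in D3.1 concerns pre/post effects within groups and is not used here.

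**Inputs that must be assumed.** True second-order r (0.60 in both groups unless stated); single-subject reliability ρ of a matrix; correlation c of the noise between two ROIs; number of matrix elements. None is in the documents.

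**Formula.** For averages over n participants, the expected second-order r is approximately

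r_obs = [r·n·ρ + c·(1 − ρ)] / [n·ρ + (1 − ρ)].

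With c = 0 this is r times the Spearman-Brown reliability n·ρ / [1 + (n − 1)·ρ].

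**Step 1: equal reliability, independent noise (c = 0), true r = 0.60.** Example at ρ = 0.05: stroke 0.60 × 1.25/2.20 = 0.341; control 0.60 × 0.75/1.70 = 0.265.

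| ρ | stroke (n = 25) | control (n = 15) | gap |
|---|---|---|---|
| 0.05 | 0.341 | 0.265 | 0.076 |
| 0.10 | 0.441 | 0.375 | 0.066 |
| 0.30 | 0.549 | 0.519 | 0.030 |
| 0.50 | 0.577 | 0.562 | 0.014 |

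**Step 2: noise shared between ROIs.** The formula is a weighted mean of r and c, so the gap takes the sign of r − c. At r = 0.60 and ρ = 0.10:
- c = 0.3: 0.521 v 0.487, gap 0.033
- c = 0.6: no gap
- c = 0.8: (1.50 + 0.72)/3.40 = 0.653 v (0.90 + 0.72)/2.40 = 0.675, reversed

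A weakly similar pair reverses sooner: r = 0.1, c = 0.3 and ρ = 0.10 give 0.153 v 0.175. The sign can therefore differ between ROI pairs in the same network.

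**Step 3: unequal reliability (c = 0, r = 0.60).** With ρ = 0.05 in stroke and 0.10 in controls, the values are 0.341 v 0.375, again reversed. The two effects cancel when the stroke odds ρ/(1 − ρ) are 15/25 = 0.6 times the control odds, for example 0.0625 against 0.10.

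**Step 4: size against sampling variation.** Simulation with the same true matrices in both groups, r = 0.60, c = 0, equal ρ of 0.05 to 0.30, and 28, 66 or 276 elements (8, 12 or 24 stimuli), 1,000 runs per setting:
- For a single ROI pair, the mean gap was about 0.03 to 0.08 and its SD 0.03 to 0.21. The stroke r was the larger in 60% to 86% of runs.
- For the mean r over all pairs of 10 ROIs (66 elements, 400 runs per setting), the gap was again 0.03 to 0.08 but the SD only 0.02 to 0.04, and the stroke mean was the larger in more than nine runs in ten. At c = 0.3 that fell to about 70% to 80%; at c = 0.6 the gap vanished and at c = 0.8 it reversed.

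**Step 5: the remedies.** With equal ρ and no true difference:
- Second-order r per participant, groups compared on Fisher z: mean difference within 0.005 of zero, type I error 3.9% to 5.7%.
- Stroke averages over 15 of the 25: mean difference within 0.02 of zero.

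With ρ = 0.05 in stroke and 0.10 in controls, neither is clean. Subsets of 15 give 0.265 v 0.375, so the gap widens from 0.034 to 0.110. The per-participant comparison rejects in 9.7% of runs.

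**The case against.** A reader might infer that the plan tests a 25-person matrix against a 15-person matrix. It does not. The correlations run between ROIs inside each group, and the stroke-control contrast is implied by Aim 1 and section B without being written into D3.2. That objection stands, and it is why the fix applies to any such comparison.

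A reader might also infer that the larger stroke group must look more strongly coupled. The documents do not support a direction. All ROIs come from the same participants and runs, and the task model lists only six motion parameters as nuisance terms, whereas the resting-state model adds cerebrospinal fluid, white-matter and whole-brain signals. Shared noise is therefore plausible. D3.4 expects lesions to vary in size and location, which could lower reliability in the stroke group. Either can cancel or reverse the gap (steps 2 and 3).

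Nor does it follow that a false group difference will be found. For one ROI pair the bias is similar to or smaller than sampling variation, and a label permutation keeping the 25/15 split held its level in the one setting tried (4.0%, 300 runs). But the plan contains no such permutation, and one would not correct the reported estimate. In summaries over many pairs the bias is less easily lost in noise.

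Finally, this is a pilot, and D3.4 already says that RSA gains from larger samples, that power may be insufficient, and that a conventional univariate analysis is included. This limits the consequences. It concerns low power, however, and does not address distortion that differs by group size.

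**Conclusion.** The concern holds in a direction-neutral form. As D3.2 is written, second-order r and the resulting ROI clusters depend on the number of participants averaged, and 25 and 15 are not interchangeable. Under equal reliability, independent noise and a true r of 0.60, the control value is lower by 0.014 to 0.076 over reliabilities of 0.50 to 0.05. Those conditions are assumptions; the documents give neither reliability nor noise correlation, and plausible departures remove or reverse the gap. An artefact of unknown sign cannot be allowed for by eye afterwards. This is a cheap improvement to a pilot analysis and does not invalidate the study.

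**What to change.** Add to D3.2 that any stroke-control comparison of second-order r or ROI clustering will use one of two forms:
- r between ROIs computed within each participant and then summarised by group; or
- stroke-group averages over random subsets equal in size to the analysable control group (for example 1,000 draws of 15 from 25), with r averaged over the draws.

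Also report the split-half or leave-one-out reliability of the matrices by group, expressed per participant so that group size does not enter. Either form removes the part of the gap due to 25 v 15. Neither removes a true reliability difference, and equal-n subsets can expose more of it, so the text should not claim to be free of bias.

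Cost: a sentence or two, a short script and no new data. The drawback is lower or noisier reported values. Within-participant r in particular is strongly attenuated when reliability is low: with independent noise, a true 0.60 becomes 0.60 × 0.05 = 0.03 at reliability 0.05 and 0.60 × 0.30 = 0.18 at 0.30.

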Imaging Parameters (sessions 3 and 4). Scanning will take place at the Center for Biomedical Imaging on the Siemens 3T Prisma. Functional and structural scanning parameters are detailed in the **NI Core**. High-resolution structural, fluid-attenuated inversion recovery (FLAIR), diffusion-weighted (DWI), and arterial spin labeling (ASL) perfusion imaging will use in-house standard sequences and will be collected from all participants in session 3. The task-based fMRI sequence will be optimized for an event-related design with a TR of 2 seconds. For the resting-state data, a TR of 0.8 seconds will be used. Task-based and resting-state imaging will be collected in session 4 with varying protocols for participants of SG and CG as described in the timeline below and explicitly detailed in the information and consent form. All MRI sequences will be accompanied by electrical recording of physiological signals from the upper body (e.g., electrocardiogram, electrodermal analyses) to support processing of MRI data and for secondary analyses examining relationships between autonomic nervous system dysfunction, brain, and behavioral outcomes.

D2. TIMELINE

Participants of both groups (stroke, control) will undergo the same protocol, which includes 4 sessions (outlined in the table below).

Session Number	Task Description	Location at Medical University of South Carolina	Approximate Time Commitment
0	Telephone Eligibility Screening 
 • Sensorimotor function screening (Appendix 1) • Cognitive screening (TICS^{26,27}) • MRI Safety Screen 	Via telephone	30 minutes
1	Consent	Stroke Recovery Research Center or remotely through electronic consent	20-30 minutes
2	Multi-system Assessment 
All participants
 
 • Pregnancy Test • EHI[§] • Questionnaires (Appendix 2)[§] • Neuro-Cognitive and emotion Assessment 
Stroke group
 
 • physical Assessment of upper-extremity sensorimotor functioning • NIH-SS 	Stroke Recovery Research Center or partly remotely [§]	3 – 3.5 hours

	
 • SIS[§] 		

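### Resting-state analysis: whole-brain signal regression followed by unsigned coherence can count induced anticorrelation as connectivity, by an unknown amount that can vary with the lesion; a sensitivity run is needed

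*Combined protocol and SAP*

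**What the plan says.** The resting-state part of D3.2 (Analysis Plan) proceeds in this order.

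- **Purpose:** "the connectivity analysis will be used to identify physiological biomarkers for recovery and potential predictors for learning efficiency".
- **Nuisance step:** "Nuisance regression will be performed to account for the effects of motion on functional connectivity". Besides the six motion parameters, the regressors are "average CSF, white matter, and whole-brain time courses, as well as the first derivatives, squares, and squared derivatives of each of these confound predictors". The whole-brain signal therefore enters as four terms.
- **Blocks:** "time courses will be divided into sub-blocks of multiples of the TR". Block length and scan length are not given. Under Imaging Parameters in D1.4: "For the resting-state data, a TR of 0.8 seconds will be used".
- **Metric:** "Connectivity will be quantified as the magnitude-squared coherence", for each pair of regions in each block.
- **Use of the result:** "Network characteristics and their temporal dynamics will then be analyzed with dynamic network statistics", following a cited approach.

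No run without the whole-brain terms is planned, and no signed or phase-aware measure is reported. Nothing checks whether the whole-brain signal is comparable across lesions. D3.4 treats varying lesion size and location as a difficulty for defining networks and plans an exploratory look at their influence, but does not link them to this regressor.

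**The concern.** The whole-brain average is built from the same signals that are then compared. Regressing it out of every region leaves residuals that must roughly balance, so regions with no true coupling acquire negative covariance. A signed measure would show this as a negative value. Magnitude-squared coherence lies between 0 and 1 and ignores sign, so an induced correlation of -0.33 is recorded as an edge of 0.11, indistinguishable from genuine positive coupling of that strength.

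In a stroke cohort the amount induced need not be constant. It depends on each network's contribution to the whole-brain mean, and a focal lesion can change that contribution. Edge values could then differ between patients for reasons unrelated to coupling. If lesion extent also relates to impairment, such a difference could pass for a recovery biomarker or a predictor of learning.

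**Working it through.** The plan gives no figure on this point, so there is nothing to reproduce. The check asks whether the mechanism works and how large it could be.

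**Inputs.** From the documents: the order of the two steps, the four whole-brain terms, the metric and the TR of 0.8 s. Assumed: K mutually independent networks with a common spectrum and no lags, their shares of the whole-brain mean, a lesion that halves one network's amplitude (variance 1 to 0.25), scan length and block length.

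**Closed form (whole-brain mean only, no regional noise).** With equal shares, let v_i be the variance of network i and S the sum of the variances. After regression:

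- residual covariance of i and j = -v_i v_j / S
- residual variance of i = v_i - v_i² / S
- coherence = r², with r the residual correlation.

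*K = 4, all intact:* S = 4; r = -0.25/0.75 = -0.333; coherence 0.111.

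*K = 4, one network halved in amplitude:* S = 3.25.

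- Intact-intact pair: r = -0.308/0.692 = -0.444; coherence 0.198.
- Lesioned-intact pair: covariance -0.25/3.25 = -0.077; lesioned variance 0.25 - 0.0625/3.25 = 0.231; r = -0.077/√(0.692 × 0.231) = -0.192; coherence 0.037.
- Mean over the three pairs of each kind: (0.198 + 0.037)/2 = 0.117, against 0.111 before.

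*Equal shares, uncoupled intact pair, all K:*

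| K | all intact, 1/(K-1)² | one network halved |
|---|---|---|
| 3 | 0.250 | 0.640 |
| 4 | 0.111 | 0.198 |
| 5 | 0.063 | 0.095 |
| 7 | 0.028 | 0.036 |
| 10 | 0.012 | 0.015 |

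Regional noise shrinks these values. With noise variance 0.5, the K = 4 pair goes from 0.040 to 0.067.

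**Unequal shares.** With shares w and unit variances, residual covariance is -w_i w_j/Σw² and residual variance is 1 - w_i²/Σw². Take K = 7 with assumed shares 0.25, 0.20, 0.15 and four of 0.10, so Σw² = 0.165.

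- Two largest networks: covariance -0.05/0.165 = -0.303; variances 0.621 and 0.758; coherence 0.195.
- Third network halved: Σw² becomes 0.165 - 0.75 × 0.0225 = 0.148, and the same pair rises to 0.270.
- Two networks with share 0.10, all intact: (0.0606/0.9394)² = 0.004, below the equal-share 0.028.

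Unequal shares therefore concentrate the artefact in the largest networks.

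**Simulation.** All four whole-brain terms regressed out, 750 volumes (600 s), regional noise variance 0.25, 400 simulated subjects per cell, coherence averaged over 0.03-0.12 Hz, true coupling zero. For K = 4 with equal shares:

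| block | regression | all intact | one halved | standardised difference |
|---|---|---|---|---|
| 600 s | yes | 0.129 | 0.165 | 0.68 |
| 600 s | no | 0.077 | 0.074 | -0.12 |
| 100 s | yes | 0.261 | 0.294 | 0.59 |
| 100 s | no | 0.224 | 0.216 | -0.17 |

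The levels without regression are estimator bias. With shared noise of variance 0.5 added, the standardised differences with regression are 0.67 (600 s) and 0.43 (100 s). For K = 7 with equal shares they lie between -0.02 and 0.13. A separate simulation with the unequal K = 7 shares (750 volumes, 300 subjects per cell) gave 0.193 against 0.225 with the whole-brain terms (0.48), and 0.104 against 0.102 without them (-0.05).

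**Scope.** The task-based model in D3.2 lists only six motion parameters as nuisance covariates, so the representational similarity analysis for Aim 1 is not touched.

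**The case against.** The strongest reply concerns size and consequence, and much of it stands.

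- **Assumed structure.** The documents give no network count, shares or lesion effect. With seven or more equal networks the effect is negligible. This stands, although equal shares are the mild case for the largest networks.
- **Pattern, not level.** Lesioned-intact edges fall while intact-intact edges rise, so mean coherence barely changes. Nobody has shown that the planned dynamic network statistics would move. This stands: what can be claimed is a shifted pattern of edges.
- **Whole-brain regression does useful work.** It removes motion and shared noise. In the K = 4 simulation, leaving shared noise in raised coherence to about 0.14-0.15 (600 s) or 0.27 (100 s) in both settings. Deleting the regressor outright has its own cost.
- **A signed measure is not a cure.** At K = 4 the signed value still moves from -0.33 to -0.44. The real part of coherency also shrinks true edges when haemodynamic lags differ: for an assumed 2 s lag, by cos(2π × 0.05 × 2) = 0.81 at 0.05 Hz and cos(2π × 0.09 × 2) = 0.43 at 0.09 Hz. Replacing the metric is a trade-off and is not requested here.

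A reader might infer that the plan will produce a false stroke-control difference. The documents do not support that: no resting-state comparison of the two groups is written out, and the stated uses are biomarkers and predictors. The supportable worry is variation with the lesion between patients. Nor does it follow that overall connectivity would be inflated in the stroke group, or that results obtained under the plan would be invalid.

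**Conclusion.** The concern holds in a limited form. As written, the resting-state analysis cannot distinguish coupling from anticorrelation induced by the whole-brain regressor, and the induced part can vary with the lesion. Under the stated assumptions, an uncoupled intact pair moves from 0.11 to 0.20 at K = 4 and from 0.03 to 0.04 at K = 7. Unequal shares make it larger for the dominant networks (0.195 to 0.270 in the example). The size in real data is unknown, and these figures show only what is possible. The exposure is confined to the resting-state biomarkers and predictors. For a proof-of-concept pilot this is a worthwhile, inexpensive improvement and not a fatal flaw.

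**What to change.** Keep the planned nuisance model and magnitude-squared coherence as the main analysis, and add to D3.2:

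1. One pre-specified sensitivity run of the resting-state pipeline that omits the whole-brain time course, its first derivative, square and squared derivative, with everything else unchanged.
2. For each edge that supports a reported biomarker or predictor, a statement of whether the coherence is in-phase or anti-phase, taken from the phase of the cross-spectrum already computed. An anti-phase label flags an edge for scrutiny. It does not by itself prove an artefact.
3. A reporting rule: a biomarker or predictor that does not persist in the sensitivity run is described as dependent on whole-brain regression.

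The cost is a few sentences and one more run on data already collected. The sensitivity version controls motion and shared noise less well, so disagreement between the two runs calls for caution in interpretation and not automatic rejection. Fixing the rule before results are seen also prevents a later choice of whichever version looks better.
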